8. ASSESSMENT OF SAFETY

8.1. *Specification of safety parameters*

The assessment of safety and tolerability is the secondary objective of this study. The assessment of safety will be evaluated by:

- Conjunctival hyperemia measured with a [REDACTED]
[REDACTED]
[REDACTED]
[REDACTED]
[REDACTED]
- Biomicroscopy of anterior segment including evaluation of cornea, conjunctiva and anterior chamber. Fluorescein staining to be used.
- Ophthalmoscopy. Dilated fundus exam including optic nerve, macula, vessels and periphery.
- Heart rate and blood pressure. Blood pressure should be measured using the same arm and same cuff size appropriate for arm circumference throughout the study. BP and heart rate should be measured after at least 3 minutes rest in the sitting position. If HR or BP are outside the normal range (see Exclusion Criteria – Systemic #7 and #8), they may be repeated only once following at least a 5 minute rest period in the sitting position.
- Adverse events.

8.2. *Assessing, recording, and analyzing safety parameters*

The timing for recording safety parameters may be found in Section 4.2, [Table 1: Schedule of Visits and Procedures](#).

8.3. *Adverse events*

All AEs and SAEs that occur following consent and until the final study visit should be collected and recorded on the AE or SAE CRF page. Only treatment-emergent adverse events/adverse reactions will be summarized (see Section 9.3.5).

All treatment-emergent adverse events/adverse reactions occurring during the study (i.e. once the subject has received one dose of study medication) **must** be documented, regardless of the assumption of causal relationship, on the respective CRF. All treatment-emergent adverse events/adverse reactions must be documented from the time the subject receives the **first dose** of study medication until the subject's participation in the study has been completed. If a subject has ongoing adverse events/adverse reactions at the time of study completion, the ongoing adverse events/adverse reactions **must** be followed-up and provided appropriate medical care until the signs and symptoms have remitted or stabilized or until abnormal laboratory findings have returned to acceptable or pre-study limits.

Documentation of adverse events/adverse reactions includes start date and stop date, severity, action(s) taken, seriousness and outcome.

8.3.1. Adverse event definitions

The following definitions of terms apply to this section:

Adverse event means any untoward medical occurrence associated with the use of a drug in humans, whether or not considered drug related.

Life-threatening adverse event or life-threatening suspected adverse reaction. An adverse event or suspected adverse reaction is considered “life-threatening” if, in the view of either the investigator or sponsor, its occurrence places the subject or subject at immediate risk of death. It does not include an adverse event or suspected adverse reaction that, had it occurred in a more severe form, might have caused death.

Serious adverse event or serious suspected adverse reaction. An adverse event or suspected adverse reaction is considered “serious” if, in the view of either the investigator or sponsor, it results in any of the following outcomes:

- Death.
- A life-threatening adverse event.
- Inpatient hospitalization or prolongation of existing hospitalization.
- A persistent or significant incapacity or substantial disruption of the ability to conduct normal life functions.
- A congenital anomaly/birth defect.

Important medical events that may not result in death, be life-threatening, or require hospitalization may be considered serious when, based upon appropriate medical judgment, they may jeopardize the subject or subject may require medical or surgical intervention to prevent one of the outcomes listed in this definition.

Suspected adverse reaction means any adverse event for which there is a reasonable possibility that the drug caused the adverse event. For the purposes of IND safety reporting, “reasonable possibility” means there is evidence to suggest a causal relationship between the drug and the adverse event. Suspected adverse reaction implies a lesser degree of certainty about causality than adverse reaction, which means any adverse event caused by a drug.

Unexpected adverse event or unexpected suspected adverse reaction. An adverse event or suspected adverse reaction is considered “unexpected” if it is not listed in the investigator brochure or is not listed at the specificity or severity that has been observed; or, if an investigator brochure is not required or available, is not consistent with the risk information described in the general investigational plan or elsewhere in the current application, as amended. “Unexpected,” as used in this definition, also refers to adverse events or suspected adverse reactions that are mentioned in the investigator brochure as occurring with a class of drugs or as anticipated from the pharmacological properties of the drug but are not specifically mentioned as occurring with the particular drug under investigation.

Any medical condition present prior to administration of the masked study medication which remains unchanged or improved should NOT be recorded as an adverse event at subsequent visits.

As noted in Section 7.2.1, any change in their Baseline health status that is not considered to be an adverse event should be recorded on the Medical History page of the CRF (e.g., the subject has been diagnosed with cancer).

The study medication relationship for each adverse event/adverse reaction should be determined by the Investigator using these explanations:

- **Not Related:** The event is clearly related to other factors such as subject's clinical condition, therapeutic interventions, concomitant disease or therapy administered to the subject and does not follow a known response pattern to the product.
- **Possibly Related:** The event follows a reasonable, temporal sequence from the time of study medication administration and/or follows a known response pattern to the study medication but could have been produced by other factors such as the subject's clinical state, therapeutic interventions or concomitant therapy administered to the subject.
- **Related:** The event follows a reasonable, temporal sequence from the time of study medication administration and/or follows a known response pattern to the study medication and cannot be reasonably explained by other factors such as subject's clinical state, therapeutic interventions or concomitant therapy administered to the subject, **and** either occurs immediately following study medication administration, or improves on stopping the study medication, or reappears on repeat exposure, or there is a positive reaction at the application site.

Intensity (severity) of an adverse event is defined as a qualitative assessment of the level of discomfort of an adverse event as is determined by the Investigator or reported to him/her by the subject. The assessment of intensity is made irrespective of study medication relationship or seriousness of the event and should be evaluated according to the following scale:

- 1 = Mild: present, but not distressing, and no disruption of normal daily activity.
- 2 = Moderate: discomfort sufficient to reduce or affect normal daily activity.
- 3 = Severe: incapacitating, with inability to work or perform normal daily activity.

A change in severity for a reported AE will require a stop date for the previous severity and a new start and stop date for the new severity. For example, a change in severity may go from mild to severe or from severe to moderate. In either case the start or stop dates should be recorded.

Action taken in response to an adverse event is coded as:

- 1=None.
- 2=Study medication interrupted.
- 3=Study medication discontinued.
- 4=Non-drug therapy.
- 5=New OTC or Rx drug added.
- 6=Hospitalized (< 24 hours).
- 7=Hospitalized (≥ 24 hours).

Outcome of an adverse event is coded as:

- 1=Recovered without sequelae.
- 2=Stable and ongoing.
- 3=Ongoing.
- 4=Death.
- 5=Unknown/ Lost to follow-up.

The term “severe” is used to describe the intensity (severity, see above) of an event/reaction; the event/reaction itself may be of relatively minor medical significance (such as severe headache). This is not the same as a “Serious” Adverse Event, which is based on subject/event outcome or action criteria usually associated with events that pose a threat to the subject’s life or vital functions. “Serious”ness (NOT severity) serves as a guide for defining regulatory reporting obligations.

In previous clinical studies of Nyxol the most frequently reported adverse event was conjunctival hyperemia. **In the present study, investigators are cautioned to use the appropriate verbatim term on the adverse event form to describe this observation:**

- **Redness related to instillation that is transient (i.e., is no longer present 2 hours after instillation) = “conjunctival erythema upon instillation”.**
- **Redness that is NOT transient (i.e., is present 2 hours after instillation) = “conjunctival hyperemia”.**

Investigators are also cautioned to appropriately note all observations of conjunctival hyperemia (also called conjunctival erythema) on the biomicroscopy CRF.

Expedited reporting of Serious and Unexpected Adverse Events: All treatment emergent SAEs (related and unrelated) will be recorded from the first administration of study medication, Baseline Visit (Day 1), until the final study visit, following the end of treatment exposure. Any SAEs “suspected” to be related to the investigational product and discovered by the Investigator at any time after the study should be reported.

Any SAE that occurs must be reported to Oculos within 24 hours of its occurrence or within 24 hours of learning of its occurrence. Recurrent episodes, complications, or progression of the initial SAE must be reported to Oculos as follow-up to the original episode within 24 hours of the Investigator receiving the information. Information about all SAEs will be collected and recorded on the SAE form. All pertinent medical records and information collected during the treatment and follow-up of the subject should be maintained at the site with a copy emailed to [contact]. The Investigator must assess the SAE relationship and complete the SAE form. Oculos may request additional information. Follow-up information (e.g., discharge summary) will be retained in the subject’s chart and a copy will be emailed to [contact]. In addition, all SAEs should be recorded on the Adverse Event CRF page with the serious question marked “Yes”.

It is the investigator’s responsibility to notify the approving IRB of any SAEs on a timely basis as instructed by the Sponsor following the Sponsor’s determination of causality. All subjects who experience an SAE should be followed clinically and undergo the appropriate diagnostic evaluations until stabilization or resolution of the event. The Sponsor/Oculos will report all SAEs to the US Food and Drug Administration (FDA) on the appropriate

schedule depending if the event is drug related or not drug related, expected, unexpected (based on the available information in the Investigator's Brochure).

Any death occurring during the study and follow up period must be reported as an SAE. For any death occurring through the end of the study, regardless of the degree of relationship to study drug, the SAE resulting in the death must be reported to Oculos. A death occurring after completion of the study including the Safety Follow-up Visits, that is not reasonably associated with study drug administration, does not require completion of the SAE form.

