7.2.3. Qualification Visit/Baseline (Day 1)

At the Qualification/Baseline Visit, the subject will be asked how do his/her eyes feel, and if there have been any changes in their medical condition, or concomitant medications since their last visit. Any adverse changes in the condition of the subject at this visit are recorded in the Medical/Ophthalmic History CRF.

At the Qualification/Baseline Visit:

- Females of childbearing potential will take a urine pregnancy test at 8AM.
- Review of concomitant medications at 8AM.
- IOP measurements using a [REDACTED] at the Baseline visit and both Treatment-study visits will be done at 8AM, 10AM and 4PM. All IOP measurements have a window of ± 15 minutes with at least 2 hours between the 8AM and 10AM assessments. IOP will be measured twice in both eyes at each timepoint. The mean value at each timepoint for the study eye will be used in efficacy assessments. If the difference in the two IOP measurements is >5 mmHg, a third measurement will be obtained, and the three values averaged.
- Pupil diameter, using a [REDACTED], near visual acuity using a standard chart held at 14 inches and distance visual acuity with ETDRS are measured at 8AM.
- Resting HR and BP are measured at 8AM and 4PM. Blood pressure, using the same arm, same cuff size appropriate for arm circumference throughout the study, and heart rate should be measured after at least 3 minutes rest in the sitting position. If HR or BP are outside the normal range (see Exclusion Criteria – Systemic #7 and #8), they may be repeated only once following at least a 5 minute rest period in the sitting position.
- Eye redness (conjunctival hyperemia) visually checked at 8AM, 10AM and 4PM using [REDACTED]
- Adverse events will be reviewed at each timepoint.

To continue in the study, the subject must have a mean IOP ≥ 22 mmHg at 8AM and ≥ 19 mmHg at 10AM and 4PM in the study eye **after the washout period** (if required) at the Qualification Visit (8AM).

Subjects may qualify in either eye. The eye with the higher IOP at the Qualification Visit at 8AM is designated as the study eye for the efficacy endpoints. In the case where both eyes have the same IOP, the study eye will be the RIGHT eye. See Section 9 for more information on statistical analysis. ALL TREATMENTS WILL BE ADMINISTERED TO BOTH EYES (O.U.).

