7.2.4. Study Day 8 ± 1 Day

On Study Day 8, the subject should bring their used dropper bottles with any unused medications with them for purposes of drug accountability. At the end of the Study Day 8 Visit the study medication box will be re-dispensed with the unopened medication.

The subjects will be asked if they had any problems with their eyes from the last visit, and if there have been any changes in their medical condition, or concomitant medications since their last visit. ***Any changes in the condition of the subject are recorded as an adverse event.***

In addition, on Study Day 8:

- Review of concomitant medications at 8AM.
- IOP measurements will be done at 8AM, 10AM and 4PM. All IOP measurements have a window of ± 15 minutes with at least 2 hours between the 8AM and 10AM assessments. IOP will be measured twice in both eyes at each timepoint. The mean value at each timepoint for the study eye will be used in efficacy assessments. If the difference in the two IOP measurements is > 5 mmHg, a third measurement will be obtained, and the three values averaged.
- Pupil diameter, near and distance visual acuity, resting heart rate and blood pressure are measured at 8AM. Blood pressure, using the same arm, same cuff size appropriate for arm circumference throughout the study, and heart rate should be measured after at least 3 minutes rest in the sitting position. If HR or BP are outside the normal range (see Exclusion Criteria – Systemic #7 and #8), they may be repeated only once following at least a 5 minute rest period in the sitting position.
- Eye redness (conjunctival hyperemia) visually checked at each timepoint using [REDACTED] scale.
- Adverse Events will be reviewed at each timepoint.

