### **10.1. Adverse Events**

Adverse events will be coded using MedDRA, Version 22.0.

Treatment-emergent adverse events (TEAEs) are defined as any adverse event that begins or worsens after initiation of the investigational product and through the subject's last study visit (study completion or early termination) or follow-up telephone call. Serious adverse events will be recorded from the date of informed consent, throughout the clinical trial.

If the onset of an AE is on or after the date of first dose of study medication, or increasing in severity after first dose of study medication, then the AE will be considered treatment-emergent.

Only TEAEs will be summarized; all AEs (TEAE, non-TEAE) will be included in a by-subject listing.

The number and percent of subjects with any TEAEs will be summarized by system organ class and preferred term by treatment group and overall. At each level of tabulation (ex. at the preferred term level) subjects will be counted only once if they had more than one such event reported during the AE collection period.

Note that in MedDRA, ocular events are coded to the SOC of “special senses”. Thus, using SOC in the summaries will provide a separation of ocular and non-ocular adverse events.

The following summary tables will be presented for TEAE data:

- Overall summary of TEAEs
- Summary table of TEAEs by SOC and PT
- Summary table of TEAEs by highest relationship level to study drug by SOC and PT (not related, possibly related, related)
- Summary table of TEAEs by maximum severity by SOC and PT (mild, moderate, severe)
- Summary table of serious TEAEs by SOC and PT
- Summary table of TEAEs leading to withdrawal from the study by SOC and PT
- Summary table of TEAEs leading to study medication discontinuation by SOC and PT

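### Protocol 7.2.3 and one sentence of 8.3.1 send possible adverse events, with a new cancer diagnosis as the example, to Medical History, against the protocol's own AE-recording rules

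*Protocol*

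**What the plan says.** The protocol gives several instructions on where, and from when, an untoward event is recorded.

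- **Section 8.3, general rule.** "All AEs and SAEs that occur following consent and until the final study visit should be collected and recorded", on the AE or SAE page of the case report form (CRF).
- **Section 8.3.1, definition.** An AE is an untoward medical occurrence associated with use of a drug, whether or not it is thought to be caused by the drug.
- **Section 8.3.1, Medical History sentence.** It cites Section 7.2.1 and states that a change from Baseline health not regarded as an AE "should be recorded on the Medical History page of the CRF (e.g., the subject has been diagnosed with cancer". The cancer diagnosis is its one example.
- **Section 7.2.3, Qualification/Baseline Visit.** The subject is asked about changes since the last visit, and then: "Any adverse changes in the condition of the subject at this visit are recorded in the Medical/Ophthalmic History CRF". The same section also has AEs reviewed at each timepoint that day.
- **Sections 7.2.4 to 7.2.7 (Days 8, 15, 16 and 22).** "Any changes in the condition of the subject are recorded as an adverse event".
- **Section 8.3.1, expedited reporting.** "All treatment emergent SAEs (related and unrelated) will be recorded from the first administration of study medication". The following paragraph requires any SAE to be reported within 24 hours and all SAEs to be entered on the AE page.
- **Synopsis and Section 7.2.2.** AEs during washout are assessed at the two-week safety check.

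SAP Section 10.1 says: "Serious adverse events will be recorded from the date of informed consent, throughout the clinical trial". It tabulates only treatment-emergent AEs (TEAEs) and lists all AEs. SAP Section 10.2.2 provides a narrative for each SAE.

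**The concern.** Safety against vehicle is a stated objective, and AEs are one of the primary safety measures. The SAP's AE tables, AE listing and SAE narratives cover events identified as AEs or SAEs. An event entered only on a history page does not reach them and does not trigger the 24-hour report.

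Two instructions point sites to the history page for events that other instructions treat as AEs. The Section 8.3.1 sentence is the more serious of the two. Its example is a diagnosis that may itself be serious, and nothing in it limits the rule to the time before dosing. Sites that follow different sections would record the same event differently.

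**Working it through.** The plan states no figure on this point, so the check sets the instructions side by side for three cases.

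| Event | Instructions that make it an AE | Instructions that send it to history |
|---|---|---|
| New cancer diagnosis after first dose | 8.3 (post-consent window; TEAEs documented whatever the cause); 8.3.1 definition; 7.2.4 to 7.2.7 | 8.3.1 Medical History sentence |
| New cancer diagnosis after consent, before first dose | 8.3 (post-consent window) | 8.3.1 Medical History sentence; 7.2.3 if found at Qualification |
| Other untoward change first reported at Qualification | 8.3; AE review within 7.2.3 | 7.2.3 history instruction |

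**Step 1: the qualifier in 8.3.1.** The sentence covers only changes that are not AEs. It offers no test for that beyond its example, and the example is an untoward medical occurrence of the kind the definition describes. A site learning from the example would conclude that a new cancer is not an AE.

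**Step 2: the period it covers.** Baseline is Day 1, so a change in Baseline health status most naturally means a change after Day 1. On that reading the sentence conflicts with 7.2.4 to 7.2.7. If it was meant for the time before dosing, it conflicts with the post-consent window in 8.3. The cross-reference does not settle which: 7.2.1 covers Screening procedures and contains no such rule. The nearest text is in 7.2.3.

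**Step 3: Qualification.** Section 7.2.3 contains both a history-page instruction for adverse changes and an AE review, and does not say how they divide. Section 8.3 leaves no room for a history-only entry for an event after consent.

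**Step 4: the time that the 7.2.3 question covers.** It asks about changes since the last visit. Washout lasts 28 to 35 days. If the safety check falls at 14 days, the interval is 28 − 14 = 14 to 35 − 14 = 21 days. Subjects who need no washout return the next day or up to 35 days later, so theirs is 1 to 35 days. These are lengths of time and do not estimate events.

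**Step 5: effect on the outputs.** A subject is randomized only after qualifying at all three IOP timepoints of the Qualification Visit. An event first reported there precedes treatment, and correct recording would add it to the AE listing (and, if serious, to reporting and narratives) but not to the TEAE tables. A post-dose diagnosis filed under the 8.3.1 sentence is different: it would be missing from the TEAE tables as well.

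**The case against.** The strongest reply is that the protocol elsewhere already requires the right thing, and most of that reply stands. A reader might draw three stronger conclusions that the documents do not support.

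- **That harms of washout are not recorded as AEs.** The synopsis and 7.2.2 assess AEs at the two-week check, 8.3 covers everything after consent, and 7.2.3 has its own AE review. What remains is mainly a harm first reported at Qualification.
- **That SAE recording starts at first dose.** The sentence in 8.3.1 is limited to treatment-emergent SAEs, which by definition cannot begin earlier. It is followed by reporting of any SAE within 24 hours, and 8.3 and SAP 10.1 both start at consent. The wording could mislead a site and deserves clarification, but it is not a separate contradiction.
- **That untoward events after consent go to history in general.** The 8.3.1 sentence is confined to changes not considered AEs, and every post-dose contact has an instruction to record changes as AEs.

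Two further replies carry some weight. The AE definition refers to use of a drug, so a pre-dose diagnosis is less plainly an AE by definition alone; it is the collection window in 8.3 that brings it in. And a history entry is not lost from the database: SAP 8.4 has medical history coded, summarized and listed. But it would be shown there as history, without the severity, action taken, seriousness and outcome that 8.3 requires for an AE.

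None of this removes the conflict over the cancer example or over the history instruction in 7.2.3.

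**Conclusion.** The point holds as an internal inconsistency in safety recording. The Medical History sentence in 8.3.1 conflicts with the AE definition and with 7.2.4 to 7.2.7, and its cross-reference is wrong. The history instruction in 7.2.3 conflicts with 8.3 and sits beside an AE review in its own section.

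Its size cannot be put as a number of events. Before dosing, the gap is mainly harms first reported at Qualification, and the effect is on completeness of listings, SAE reporting and narratives. These events precede randomization and do not bear on the between-arm TEAE tables. After dosing, the 8.3.1 sentence could remove a possibly serious treatment-emergent event from those tables too, if a site follows it in preference to the visit sections.

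The conclusion assumes that sites act on the written text. The schedule table and the CRF pages are not in the material available, and forms or site instructions might already resolve the routing. The correction is still warranted, because a site obeying the protocol as written could misfile a serious event and the change costs almost nothing.

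**What to change.** 1. **Section 8.3.1, Medical History sentence:** delete it, or limit it to conditions diagnosed before consent. Remove the cancer example and the reference to 7.2.1. State that any new diagnosis after consent is an AE and is assessed for seriousness.
2. **Section 7.2.3:** send untoward changes since consent to the AE page, in line with 8.3.
3. **Section 8.3.1, expedited reporting:** make clear that first dose marks only the treatment-emergent label, and that all SAEs are recorded and reported from consent, as 8.3 and SAP 10.1 say.
4. **Reporting:** keep AEs before first dose out of the TEAE tables and list them as pre-treatment AEs. SAP 10.1 already lists non-TEAEs.

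The cost is wording in three places, a note to sites and a few more pre-treatment AEs in the listing. No visit, procedure or change to sample size is needed.
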